3. INVESTIGATIONAL PLAN

3.1. Overall Study Design and Plan

This is a multi-center study to evaluate the safety, tolerability, PK, [REDACTED] and clinical activity of EQ001 in subjects with an initial clinical presentation of aGVHD. The study will enroll up to approximately 100 subjects in two (2) parts [REDACTED]

- Part A – Open-label, cohort based, dose escalation component:

Part A will enroll approximately 24 subjects in successive cohorts of 3 to 6 adult subjects each to determine the safety, tolerability, pharmacological, and biological activity of ascending IV doses of EQ001. Once an optimal dose is determined in Part A of the study, up to approximately 15 additional subjects will be enrolled at the selected dose in order to collect more data.

- Part B – Randomized, double-blind, placebo-controlled component:

[figure not shown]
Part B will enroll approximately 60 additional subjects, randomized in a 2:1 ratio to either active treatment with an optimally defined dose of EQ001 (40) or placebo (20), to determine the safety, tolerability, and clinical activity of EQ001.

Part A of the study will utilize a standard 3 + 3 dose escalation design until a dose is selected. Cohort enrollment will proceed in a sequential manner to evaluate the escalating dose levels of EQ001 (Section 5.3.1). Dose escalation will proceed as long as no predefined stopping criteria are met. The dose-limiting toxicity (DLT) assessment period will be the first 29 days of treatment (i.e., Study Days 1 to 29) and will guide dose escalation decisions. Subjects will be considered evaluable for DLT assessment if they have received at least two doses of study drug and completed through Study Day 29 or received at least one dose of study drug and had a DLT within the first 29 days on study. Enrollment of the next higher dose cohort will not commence until all safety data from all subjects from prior cohorts and all available safety data from the current cohort through Study Day 29 are reviewed by the Data and Safety Monitoring Committee (DSMC) and approval is granted for dose escalation. An optimal dose of EQ001 will be determined based on all available data, including safety, tolerability, [REDACTED]. Once a dose is selected, up to approximately 15 additional subjects will be enrolled at the selected dose in order to collect more data.

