7. ADVERSE EVENTS

An AE is any unfavorable and unintended sign (including an abnormal laboratory finding), symptom, or disease or any worsening of a pre-existing condition temporally associated with the use of a study drug, whether or not related to the study drug. AEs that occur after the first dose of EQ001 or during the study treatment and safety follow-up periods will be documented on the AE eCRF. The investigator will assess the AE severity and relationship of the AE to study drug. The investigator will treat the subject as medically required.

Laboratory values that are outside the laboratory reference range should be reported as AEs only if considered clinically significant by the investigator.

From the time of obtaining informed consent through the first administration of study drug, all SAEs and nonserious AEs related to protocol mandated procedures will be recorded on the SAE/AE eCRF. All other untoward medical occurrences observed during screening, including exacerbation or changes in medical history, will be captured on the medical history eCRF. Details on recording and reporting AEs are provided below.

AEs will be collected through Study Day 169 for subjects who complete study drug through Day 57. AEs will be collected through Study Day 85 for subjects who discontinue study drug early. Recent hospitalizations and SAEs, if applicable, will be recorded at the Day 253 and 337 visits.

The investigator's clinical judgment should be used to determine whether a subject is to be withdrawn due to an AE. In the event the subject requests to withdraw from study-related treatment, the subject should be asked to return for all remaining study visits through Study Day 169. In the event a subject is withdrawn from study, an early-termination visit should be completed.

All subjects experiencing AEs while on study drug, including clinically significant abnormal laboratory values, whether or not associated with use of the study drug, must be monitored until the condition returns to normal, returns to the subject's baseline, until the investigator determines the AE has reached a stable outcome and is no longer clinically significant, or the subject is considered lost to follow up.

If consent has not been withdrawn, all deaths should be reported through Study Day 337, even if study drug has been discontinued.

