9.9. Efficacy Analyses

[REDACTED]

[REDACTED]

[REDACTED]

[REDACTED]

[REDACTED]

[REDACTED]

[REDACTED]

All efficacy data summaries for Part A will use the safety population, whereas Part B will use the efficacy population for Part B. Clinical activity will be assessed by change from baseline in: aGVHD Organ Stages and Overall Clinical Grading and aGVHD-AI. Corticosteroid and immunosuppressive agent usage will be compared between groups. Overall mortality and nonrelapse-mortality at 12 months, overall response rate (proportion of subjects with a best response of PR or better during the 12-month assessment period compared to last pre-dose assessment) and Kaplan-Meier estimates of progression-free survival will also be calculated. In general, changes from baseline in numeric variables will be compared between the two groups using an analysis of covariance model with baseline value as a covariate. Proportions will be compared between the groups using the Fisher's Exact test. Time to event data will be compared using the log-rank test.

[REDACTED]

[REDACTED]

[REDACTED]

[REDACTED]

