6.9.6 Overall Survival

Overall survival (OS) is defined as time from first dose to death from any cause. For subjects who are alive at the time of analysis, OS will be calculated as the time from first dose to last known alive date and will be considered as censored. OS in days will be calculated as:

$$(\text{Death date or censoring date} - \text{first dose date} + 1)$$

OS data will be summarized similar to PFS data.

In addition to the safety population, this analysis will also be conducted using the evaluable population, the safety population for subjects with ≤ 3 day of systemic steroid dosing prior to dosing of study medication, and the safety population for subjects with > 3 day of systemic steroid dosing prior to dosing of study medication.

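### Part B mortality, in the visible text of Protocol Section 9.9, reads as a crude 12-month proportion under Fisher's exact test with no censoring rule; censored overall survival with the log-rank test is the better analysis

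*Protocol*

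**What the plan says.** Protocol Section 9.9 lists "Overall mortality and nonrelapse-mortality at 12 months" next to an overall response rate that it defines as a proportion. The same sentence adds that "Kaplan-Meier estimates of progression-free survival will also be calculated". Two general rules follow: "Proportions will be compared between the groups using the Fisher's Exact test" and "Time to event data will be compared using the log-rank test". Neither rule names mortality. The visible text gives Part B no overall survival endpoint, no censoring rule, and no rule for subjects whose status at 12 months is unknown. Section 9.9 has redacted blocks before and after this text, and the SAP supplied covers Part A only.

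On follow-up, Protocol Section 7 states: "If consent has not been withdrawn, all deaths should be reported through Study Day 337". Section 3.1 schedules telephone contacts on Days 253 and 337.

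For Part A, SAP Section 6.9.6 defines overall survival from first dose to death from any cause. For subjects still alive, "OS will be calculated as the time from first dose to last known alive date and will be considered as censored". The summary follows that of progression-free survival (SAP 6.9.2), which is Kaplan-Meier.

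Part B efficacy summaries use the efficacy population, meaning subjects with at least three doses (Protocol 9.3.4 and 9.9).

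**The concern.** Mortality is the least subjective outcome in Part B. A fixed-time proportion needs every subject's status at the cut-off. Death reporting stops if consent is withdrawn, so some statuses may be unknown. A crude proportion then has two choices:

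- count such subjects as alive, which biases mortality down;
- drop them, which biases it up, because a subject who dies before being lost stays in while one lost alive leaves.

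If loss differs between arms, the difference between arms is distorted too. The proportion also ignores when deaths occur, and Fisher's exact test is conservative with 20 controls. The single-arm part of the same study already treats survival as a censored outcome.

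**Working it through.** The visible text gives no mortality rate, effect size, loss rate or power, so there is no figure of the plan to reproduce. Those inputs are assumptions below. The sample sizes, 40 EQ001 and 20 placebo, are from Protocol 3.1.

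**1. Bias from loss.** Let p be true mortality at the last contact, with exponential deaths, so λ = −ln(1 − p) on a period of length 1. Let a fraction L be subject to loss at a uniform time.

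- Chance that a death is seen before loss: 1 − p/λ.
- Lost counted as alive: m = (1 − L)p + L(1 − p/λ).
- Lost dropped: m / (1 − L·p/λ).

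Take 40% placebo mortality with 20% loss, and 20% EQ001 mortality with 10% loss.

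- Placebo: λ = 0.511 and p/λ = 0.783. Counted as alive: 0.8 × 0.40 + 0.2 × 0.217 = 0.363. Dropped: 0.363/(1 − 0.157) = 0.431.
- EQ001: λ = 0.223 and p/λ = 0.896. Counted as alive: 0.9 × 0.20 + 0.1 × 0.104 = 0.190. Dropped: 0.190/(1 − 0.090) = 0.209.

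A true 40% versus 20% (20 points) thus reads as 36% versus 19% (about 17 points) or 43% versus 21% (about 22 points).

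**2. Power.** Two-sided 5%, exponential deaths, 10% lost uniformly in each arm, lost counted as alive for Fisher. The hazard ratio is ln(1 − EQ001 mortality)/ln(1 − placebo mortality). The two power columns come from separate simulations, with 4,000 and 6,000 trials per scenario.

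| Placebo / EQ001 mortality | Hazard ratio | Fisher vs log-rank (4,000) | Fisher vs log-rank (6,000) |
|---|---|---|---|
| 40 / 20% | 0.44 | 31% vs 40% | 30% vs 39% |
| 50 / 25% | 0.42 | 43% vs 52% | 42% vs 50% |
| 40 / 15% | 0.32 | 48% vs 59% | 47% vs 58% |
| 30 / 10% | 0.30 | 42% vs 49% | 42% vs 50% |

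The gaps are 7 to 11 points. For smaller effects they shrink: 40/30% (hazard ratio 0.70) gives 3 to 4 points, 30/20% (0.63) about 5, and 20/10% (0.47) 3 to 4. Together that is about 3.5 to 5.5 points. With the unequal loss of step 1, power at 40/20% is 24 to 26% for Fisher and 37 to 39% for log-rank.

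**3. Where the gap comes from.** With no loss at all, 40/20% gives 33% versus 41%, so 8 of the roughly 9 points are already there. Fisher's true size in these settings is about 3.2 to 3.6%, against about 5% for log-rank. Compared with an uncorrected chi-square test on the same proportions, log-rank gains only 2 to 3 points without loss. The gap is mostly Fisher's conservatism.

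**4. Sensitivity.** Over a wider grid (placebo mortality 30 to 70%, hazard ratio 0.3 to 0.6, loss 0 to 20%) the gap runs from about 5 to 17 points. The Schoenfeld approximation gives a smaller one, about 1 to 7 points. For example, at 50% placebo mortality and hazard ratio 0.5, expected deaths are 20 × 0.50 + 40 × 0.293 = 21.7. Power is then Φ(0.693 × √(21.7 × 1/3 × 2/3) − 1.96) = 33.1%, against 31.1% for Fisher by exact enumeration. In simulation the same case gives 38.8% versus 31.4%.

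**5. Analysis set and time point.** With dosing every 14 days, the third dose falls on Day 1 + 2 × 14 = 29. A subject who dies before then cannot enter the efficacy population. If time starts at first dose, as in SAP 6.9.6, a survival curve in that population has no deaths in its first 28 days by construction. Separately, the last contact, Day 337, is 337/365.25 × 12 = 11.1 calendar months, so 12 months needs a stated day.

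**The case against.** The strongest reply is that the protocol never assigns Fisher's test to mortality. It gives two general rules, and a Kaplan-Meier estimate at 12 months with a log-rank comparison would also fit the words. Redacted text or a Part B SAP may settle it. This stands as a limit on the finding: the crude proportion is the natural reading, not a stated rule.

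Three stronger readings are tempting and are not supported.

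- A reader might infer that subjects will in fact be miscounted. The documents give no dropout figure and ask for all deaths through Day 337 unless consent is withdrawn, even off study drug. The bias is conditional on loss.
- A reader might infer that Part A already uses Kaplan-Meier with a log-rank test. The Part A SAP has Kaplan-Meier only and also reports deaths as counts and percentages (SAP 6.10.5). The log-rank test appears in Protocol 9.9.
- A reader might take 7 to 11 points as the general cost. It holds for assumed hazard ratios of about 0.30 to 0.44, and loss explains little of it.

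It is also fair that Part B is exploratory, that power stays below 60% with either test in every scenario tabulated, and that Kaplan-Meier relies on loss being unrelated to prognosis. The simulations use all 60 subjects, so the planned three-dose set would have less power still. None of this favours leaving the crude proportion in place.

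**Conclusion.** The concern holds in a limited form. In the visible text, Part B mortality reads as an uncensored proportion under Fisher's exact test, and a better analysis is available from methods the two documents already contain. The power gain is about 3.5 to 5.5 points at 40/30, 30/20 and 20/10% mortality, and about 7 to 11 points for larger effects such as 40/20 or 40/15%. It rests on assumed exponential deaths, 40 versus 20 subjects, a two-sided 5% level and 0 to 10% loss, and it is due mainly to Fisher's conservatism. The bias from unknown vital status is a few points under the loss rates assumed here and zero if no one is lost. The change is worth making because it is cheap and removes an analyst's choice on the hardest outcome, but it does not turn Part B into a well-powered mortality comparison.

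**What to change.** In Section 9.9, or in the Part B SAP:

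- Define Part B overall survival as time from first dose to death from any cause, censored at last known alive date as in SAP 6.9.6. Compare arms with the log-rank test, and take overall mortality out of the outcomes tested by Fisher's exact test.
- Report mortality at Day 337 in each arm as 1 minus the Kaplan-Meier estimate, with a confidence interval for the difference, and name that day in place of 12 months.
- Run this on all randomized and dosed subjects, not on the three-dose efficacy population.
- Report non-relapse mortality as a cumulative incidence with relapse as the competing event.

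The cost is a few sentences and a little more analysis work. Deaths are already to be reported through Day 337, and the Part A survival analysis already relies on last known alive dates. The log-rank test is less efficient if hazards cross, which is a reason to report the Day 337 difference beside it.

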10. ADMINISTRATIVE CONSIDERATIONS

10.1. Investigator Responsibilities

The investigator is responsible for complying with all local, state, and federal regulations relating to performing clinical research with an investigational product. The investigator is responsible for ensuring that the investigation is conducted according to the signed Investigator Agreement (FDA Form 1572), the approved protocol, and applicable regulations for protecting the rights, safety, and welfare of study subject under the investigator's care. The investigator is additionally responsible for the control of investigational product and for providing accurate and verifiable data to the Sponsor.

The investigator must obtain the Informed Consent and HIPAA authorization of each subject before participation in the study. The investigator must assure initial and continuing review of the study by an IRB that complies with applicable national and local regulations.

The investigator will maintain minutes of meetings with study staff and document training of research study personnel for conduct of the study, including qualifications, experience, and study role.

The investigator will be given a copy of the most current version of the EQ001 Investigator's Brochure and appropriate study process manuals and plans. The investigator is obligated to become familiar with all sections of these documents prior to initiation of the study.

Other investigator responsibilities relative to the IRB include the following:

- Submit to the IRB for review any advertisements that will be used to recruit subjects
- Submit all protocol amendments, revisions of the Investigator's Brochure, or revisions of the Informed Consent to the IRB for review
- If Sponsor notifies the investigator about SAEs reported in other studies associated with this investigational product, report that information to the IRB
- Provide the IRB with any other information it requests before or during the conduct of the study
- Report to the IRB all adverse drug reactions that are serious, unexpected, and related to investigational product
- Maintain a file of study-related information
- Update the IRB on a minimum of a yearly basis

10.2. Institutional Review Board (IRB) Approval

Before initiation of the study at a study site, the protocol, including the final version of the ICF, the subject information sheet (if applicable), and any other relevant study documentation will be submitted to the appropriate IRB. In addition, the IRB must approve all advertising used to recruit subjects for the study. Written approval of the study documentation, including any proposed postings or advertising, must be obtained and sent to the Sponsor or its designee before the study site can be initiated or the study drug can be released to the investigator.

The investigator is responsible for informing the IRB of any amendments to the protocol, ICF, written information provided to subjects, and/or other procedures in accordance with local requirements. The protocol must be re-approved by the IRB upon receipt of amendments, in accordance with applicable law. The investigator must send a copy of the approval letter from the IRB to the Sponsor or its designee.

The investigator will report promptly to the IRB and the Sponsor any new information that may adversely affect the health or safety of past or current subjects or the conduct of the study, including deviations from the protocol or reports of any reportable SAEs, during and for two (2) years after completion of the study.

The investigator should submit written reports of clinical study status to their IRB annually or more frequently if required. A final study notification will also be forwarded to the IRB after the study is completed or in the event of premature termination of the study in accordance with the applicable regulations. After completion of the study, the investigator will provide the IRB with a report of the outcome of the study. Copies of all contact with the IRB should be maintained in the study file. Copies of clinical study status reports (including termination) should be provided to the Sponsor.

10.3. Ethical Conduct of the Study

This study will be conducted in compliance with the protocol; GCP guidelines, including International Council for Harmonisation (ICH) of Technical Requirements for Registration of Pharmaceuticals for Human Use Guidelines (ICH E6); and FDA regulatory requirements. In addition, the study will be conducted in compliance with any and all current laws, requirements, regulations (including, but not limited to, HIPAA) of local, state, federal and foreign authorities and agencies having jurisdiction over the subject matter and performance of, and the study (referred to herein as “applicable law”).

Investigators and all sub-investigators will comply with 21 Code of Federal Regulations (CFR), Part 54, 1998 and similar conflicts of interest laws requiring documentation of financial interests or arrangements with the Sponsor, or proprietary interests in the drug under study. Any required documentation must be provided prior to the investigator’s (and any sub-investigator’s) participation in the study. The investigator and sub-investigator(s) will notify the Sponsor or its designee of any change in reportable interests during the study and for 1 year following completion of the study. Study completion is defined as the date when the last subject completes all protocol-defined activities.

10.4. Subject Information and Consent

Prior to conducting any study-related procedures, the investigator must obtain written informed consent from each subject or legally authorized representative, in accordance with applicable law. Consent will be documented on a written ICF. The ICF must be approved both by the Sponsor and by the reviewing IRB prior to presenting it to a subject. Each ICF must comply with the ICH GCP Guidelines, FDA requirements, and local regulatory requirements.

Investigators may discuss study availability and the possibility for entry with a potential subject without first obtaining consent. However, informed consent must be obtained and documented prior to initiation of any procedures that are performed solely for the purpose of determining eligibility for research, including withdrawal from current medication(s). The informed consent process should take place under conditions where the subject has adequate time to consider the risks and benefits associated with his/her participation in the study. The investigator or qualified designee must explain to each subject or legally authorized representative the aims, methods, reasonably anticipated benefits, and potential hazards of the study.

Once appropriate essential information has been provided and fully explained in layman's language to the subject by the investigator (or a qualified designee), the approved ICF will be signed and dated by both the subject and the person obtaining consent (investigator or designee), as well as by any other parties required by the IRB. The subject will receive a copy of the signed ICF; the original will be retained in the study files. The investigator must document the consent interview and place the record in the study files. The investigator shall also maintain a log of all subjects who sign the ICF and indicate if the subject was enrolled into the study or reason for non-enrollment.

10.5. Confidentiality

The investigator must assure that subjects' anonymity will be strictly maintained and that their identities are protected from unauthorized parties. Only subject initials, date of birth, another unique identifier (as allowed by local law) and an identification code will be recorded on any form or biological sample submitted to the Sponsor, IRB, or laboratory. Laboratory specimens must be labeled in such a way as to protect subject identity while allowing the results to be recorded to the proper subject. Refer to specific laboratory instructions (or in accordance with local regulations). NOTE: The investigator must keep a screening log showing codes, names, and addresses for all subjects screened and for all subjects enrolled in the study. Subject data will be processed in accordance with all applicable regulations. (Some studies may require double-coding of samples; insert language as appropriate.)

The investigator agrees that all information received from the Sponsor, including but not limited to the Investigator's Brochure, this protocol, CRF/eCRF, the study drug, and any other study information, remain the sole and exclusive property of the Sponsor during the conduct of the study and thereafter. This information is not to be disclosed to any third party (except employees or agents directly involved in the conduct of the study or as required by law) without prior written consent from the Sponsor. The investigator further agrees to take all reasonable precautions to prevent the disclosure by any employee or agent of the study site to any third party or otherwise into the public domain. In compliance with applicable law and/or ICH GCP Guidelines, the investigator will permit the Sponsor's representatives and, when necessary, representatives of the FDA or other regulatory authorities' direct access to any medical records relevant to the study for verification of study-related procedures and data. Direct access includes examining, analyzing, verifying, and reproducing any records and reports that are important to the evaluation of the study.

Investigators will obtain authorization from the subject to permit access to study-related records, including personal information.

The Sponsor will ensure that the use and disclosure of protected health information obtained during the study complies with HIPAA and related privacy laws, including the Health Information Technology for Economic and Clinical Health Act, where these rules are applicable. Authorization is required from each subject (i.e., specific permission granted by such individual to a covered entity for the use or disclosure of an individual's protected health information). The investigator and institution must obtain such waiver/authorization in writing from the subject or legally authorized representative. Valid authorization must meet the implementation specifications under the applicable privacy laws. Authorization may be combined in the ICF (approved by the IRB), or it may be a separate document (approved by the IRB) or provided by the investigator or Sponsor (without IRB approval).

